A recent retrospective study analyzing the data from a large US administrative database showed that the majority of prostate cancer patients received warfarin for VTE treatment with an equal proportions of patients receiving LMWH and NOACs, of which rivaroxaban was mostly common. Reduced hazard of bleeding for NOACs versus warfarin and for NOACs versus LMWH was observed (6). An analysis of RIETE Registry showed a relatively low risk of bleeding but a substantial rate of VTE recurrences in PCa patients (7); however the patients' sample was limited and geographically diverse due to the nature of the Registry.

Rivaroxaban (Xarelto) is indicated for the treatment of DVT, PE and prevention of recurrence; its label that does not have a warning regarding its use in patients with active cancer. Demonstrating opportunities for use of oral anticoagulants such as rivaroxaban in cancer patients is thus essential.

The on-going 'Cancer Associated thrombosis – expLoring soLutions for patients through Treatment and Prevention with RivarOxaban' (CALLISTO) programme encompasses several initiatives, including both clinical trials as well as non-interventional studies and a survey. Nevertheless, several gaps in knowledge remain as some of the research questions will not be feasible to answer within the planned activities. Real-life data reflecting current practice are needed to address those gaps. In particular, there is a need to describe:

- Clinical characterization (staging, presence of metastasis, types of cancer therapy etc.) of cancer patients with an emphasize on most common cancers (prostate, lung, breast, colorectal etc.) in order to understand risk of thrombotic and bleeding events in this population.
- AC treatment of patients with cancer experiencing an acute VTE event, its duration, dose variation and switching against the background of different cancer treatment in order to understand prescription patterns of clinicians.
- Risk of recurrent thrombotic and bleeding events after the initiation of different AC therapies.

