9.2.3 Selection criteria from PCBaSe

PCa patients

Inclusion criteria

Initially all patients newly diagnosed with PCa between 2007-2016 with at least one year before the end of follow up date (31 December 2017) will be included.

From this population, a sub-population of PCa patients with a first cancer-related VTE event will be selected.

Exclusion criteria

No exclusions will be made.

Men without PCa

Inclusion criteria

All PCa-free men included in PCBaSe who are randomly selected from the general population of Sweden with the same birth year and county of residence of PCa patients diagnosed between 2007-2016.

Exclusion criteria

A PC free men diagnosed with a prostate cancer during the follow up will be identified and censored.

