9.3 Variables

Baseline is defined as:

- in men with PCa: a date of an incident PCa
- in PCa-free men: a date of selection of PCa-free men (who are alive) into the database corresponding to the date of diagnosis for the index case

Index date is defined as:

- in men with PCa:
 - a date of a first cancer-related VTE event that is a VTE event related to the diagnosis of PCa (to define the relatedness, different time-frames will be specified and applied);
- in PCa-free men:
 - a date of selection into the database for defining a first recorded VTE event.

9.3.1 Characteristics of PCa and (where possible) PCa-free men:

- Age at PCa diagnosis
- Age at VTE
- Charlson Comorbidity Index (CCI) based on discharge diagnosis (including variables included into CCI)
- Specific events at baseline (that occurred prior and at the baseline) define by ICD codes for:
 - intracranial bleeding
 - gastrointestinal bleeding
 - urogenital bleeding
 - ischaemic heart disease
 - myocardial infarction

- heart failure
- stroke (ischaemic and haemorrhagic)
- transient ischaemic attack
- atrial fibrillation
- renal impairment
- renal failure
- depression
- hypertension
- hyperlipidaemia
- diabetes
- asthma
- COPD
- other cancers than PCa
- previous VTE events
- Co-medications at baseline (120 before the index event) and during follow-up (from index date)
 - Antiplatelets
 - Proton pump inhibitors
 - NSAIDs
 - SSRIs
 - Oral steroids
 - Antibiotics
 - Lipid-lowering medications
- PCa/specific parameters:
 - County
 - Hospital type (university, non-university)
 - Clinical TNM staging
 - PSA (at time of PCa diagnosis)
 - PCa risk categories (defined at diagnosis according to a modification of the National Comprehensive Cancer Network Guideline):
 - a. Low-risk: T1-2, Gleason score of 2–6 and PSA < 10 n/ml
 - b. Intermediate-risk: T1-2, Gleason score 7 and/or PSA 10–20 ng/ml
 - c. High-risk: T3 and/or Gleason score 8–10 and/or PSA 20–50 ng/ml

- d. Regionally metastatic T4 and/or N1 and/or PSA 50–100 ng/ml
 - e. Distant Metastatic disease: or M1 and/or PSA > 100 ng/ml; however PSA cutoff to be discussed
- Anti-cancer therapies that are delivered by a filled out-patient prescription

9.3.2 For patients in the VTE sub-population:

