The outcome of interest is therapy with anticoagulants dispensed from pharmacies (no information is available on drugs delivered in- hospital), hence the analysis focuses on anticoagulant therapies for which an out-patient prescription has been filled, i.e. long-term therapy. A full list of the treatments with their relative ATC codes is found in Annex 3. The anticoagulation treatments that will be assessed include:

1. LMWH (after hospital discharge, long-term use)
2. VKAs
3. NOACs

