9.4 Follow up

9.4.1 Exposure to anticoagulants

The exposure to AC treatment will be defined in two ways:

- the first is by following the patients until the end of the follow-up time, regardless if they are still on the drug or not.
- the second way is to follow up the patients until the filled prescription for each respective drug expires (“on/treatment”).

A grace period of 90 days will be used to define a new prescription of anticoagulant. The duration of a prescription will be derived from the median number of days between consecutive respective prescriptions after the grace period has passed.

The treatment exposure can then be used to study the switching of treatments and the discontinuation of treatments.

A start date will be defined as the date of the dispensed prescription for patients receiving anticoagulation.

Patients will be censored at earliest date of:

- Time of first occurrence of a recurrent VTE event or a bleeding event (major bleeding event i.e. intracranial, gastrointestinal, urogenital bleeding, or other bleeding leading to hospitalisation) or death
 - Patients will be followed until occurrence of one of the above mentioned outcomes of interest; similarly, the analysis is repeated in the same way for the other outcomes of interest. Therefore, the patients were not censored at the first outcome of interest and outcomes on treatment after the first is also taken in to account. Only first-time events of the same type are considered.
- End of observation time (data lock point for the database at 31st October 2017)
- Treatment discontinuation
- Treatment switching patients who switched will be censored at the time of the date of a filled prescription from a pharmacy of the new drug.

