9.8 Data analysis

Descriptive statistics will be used to define the socio-demographic and clinical characteristics (including main types of cancer therapies) of all PCa patients at the time of PCa diagnosis (Objective 1 and 3) and PCa-free men at the time of inclusion in PCBaSe (Objective 8) and include variables of interest listed above.

All categorical variables will presented by counts and proportions and continuous variables by mean, standard deviation, range, median, and first and third quartiles.

The occurrence will be estimated by calculating an incidence rate (accompanied by 95% CI) of cancer-related VTE events, split into PE and DVT events, in men with PCa (Objective 2) and in PCa-free men (Objective 10). The incidence rate is defined as the number of events of interest divided by the total number of person-years at risk. In men with PCa, the person-time at risk will be calculated from date of incident PCa diagnosis up until an outcome of interest, death or end of follow-up, whichever came first. The occurrence will be also described by Kaplan-Meier curves in different strata within different time-periods.

The AC treatment received by the PCa patients after a first cancer-related VTE event on an out-patient long-term basis will be reported by type of anticoagulation (LMWH, VKAs and NOACs) and its estimated duration (from the time-point of a hospital discharge up to 3 months, 3-6 months, more than 6 months) (Objective 4).

Time at risk for Objectives 5, 6 and 7 (recurrent VTE, bleeding leading to hospitalisation or death) will be calculated from first cancer-related VTE (the time-frame of defining cancer-relatedness will be specified later) for each events of interest up until event, death or end of follow-up.

The 95% CI for the incidence rate will be calculated using the Poisson distribution.

Incidence rates of recurrent VTE, bleedings and death will be calculated by the type and duration of AC treatment (stratification variables); however no comparative analysis of outcomes in three sub-groups of AC treatments, is planned.

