9.10 Limitations of the research methods

The main limitation of this study is that only drugs dispensed to patients via a pharmacy are recorded. This means that anti-coagulation treatments and anti-cancer treatments delivered in-hospital are not recorded in the database. Therefore, as these patients with VTE events and cancer are at high risk of being hospitalized, we will likely be missing data on their prescribed anti-coagulation treatments during their in-hospital period. However, given that treatment for VTE is usually a minimum of three months will be captured by the ensuing out-patient treatment that includes filling of prescriptions.

Another limitation is that there are no data on height and weight or lifestyle factors such as smoking status, alcohol use.

No information on adherence to the drug treatment is available directly. Therefore, dates of starting and stopping exposure to anticoagulation medications may not be fully accurate, hence we have applied two ways of defining drug exposure to account for this.

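### Anticoagulant use already under way before the VTE is not a listed variable, so Objectives 4 to 7 do not separate it from treatment started for the VTE

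*Protocol*

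**What the plan says.** The relevant rules are spread over five sections of the Protocol.

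- **Population (9.2.3).** For men with prostate cancer, "No exclusions will be made". The VTE sub-population is selected only on having a first cancer-related VTE.
- **Treatment of interest (9.3.2).** No in-hospital drug data exist, "hence the analysis focuses on anticoagulant therapies for which an out-patient prescription has been filled, i.e. long-term therapy". Indication plays no part in the definition.
- **Covariates (9.3 and 9.3.1).** AF and previous VTE are listed among events before or at baseline, and baseline in these men is the date of prostate cancer diagnosis. Drug history is given as "Co-medications at baseline (120 before the index event) and during follow-up (from index date"), followed by seven classes. Anticoagulants are not among them.
- **Exposure (9.4.1 and 9.4.3).** "A start date will be defined as the date of the dispensed prescription for patients receiving anticoagulation". In addition, "A grace period of 90 days will be used to define a new prescription of anticoagulant". Under the refill method in 9.4.3, treatment runs on between fills unless the gap exceeds six months.
- **Analysis (9.8).** For Objective 4, "The AC treatment received by the PCa patients after a first cancer-related VTE event on an out-patient long-term basis will be reported by type of" anticoagulant and by duration, counted from hospital discharge. Rates for recurrence, bleeding and death are stratified by drug class and duration only.

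The limitations in 9.10 argue that "treatment for VTE is usually a minimum of three months will be captured by the ensuing out-patient treatment". They do not mention fills made for another reason.

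**The concern.** Some men will already be taking an anticoagulant when the VTE occurs, for AF, an earlier VTE or another reason. Their fills after the VTE look the same in dispensing data as fills that begin because of it. Two results are affected.

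- **Objective 4.** Use that was open-ended before the VTE falls into the longest duration category and reads as extended VTE treatment. Section 7 says that reliable data on therapy beyond 6 months are lacking, so this category will attract attention.
- **Objectives 5 to 7.** Rates by drug and duration combine men who started at the VTE with men who had already tolerated the drug, or whose VTE occurred while they were taking it. Among the knowledge gaps, Section 7 lists "Risk of recurrent thrombotic and bleeding events after the initiation of different AC therapies". Men already on the drug cannot show risk after initiation.

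**Working it through.** **1. The plan's own figures.** The Protocol gives no figure for prior anticoagulant use. Its only precision figures are in Table 1 of 9.6, and they reproduce. In the 3% row, 1.96 × √(0.03 × 0.97 / 98 000) = 0.107 points, so the limits are 2.893 and 3.107 and the width is 0.214. The table gives 2.89, 3.11 and 0.22, which agrees within rounding of the limits. The table matters here only for its possible VTE counts: 980, 2940 and 4900 at 1%, 3% and 5%.

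**2. One man followed through the rules.** He develops AF after his prostate cancer diagnosis, takes a VKA without a planned end, and then has a DVT.

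- 9.2.3 keeps him in the sub-population.
- 9.3.1 does not flag his AF, which arose after baseline, and does not list his VKA.
- 9.3.2 counts his next fill as long-term therapy.
- The refill method in 9.4.3 treats him as continuously exposed.
- 9.8 counts duration from discharge and places him beyond 6 months.

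Had his AF been known at diagnosis, he would be flagged in the baseline table, but his place in Objectives 4 to 7 would be the same.

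**3. Effect on the share treated beyond 6 months.** Let q be the share of treated men who are prior users and p the true share beyond 6 months among new starters. If all prior users continue beyond 6 months, the reported share is (1 − q) × p + q and the shift is q × (1 − p). Neither q nor p is in the document. Assume q = 5% to 20% and p = 40%.

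| q | Reported share | Shift | Prior users within the stratum beyond 6 months |
|---|---|---|---|
| 5% | 0.95 × 0.40 + 0.05 = 43% | 3 points | 0.05 / 0.43 = 12% |
| 10% | 0.90 × 0.40 + 0.10 = 46% | 6 points | 0.10 / 0.46 = 22% |
| 20% | 0.80 × 0.40 + 0.20 = 52% | 12 points | 0.20 / 0.52 = 38% |

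With p anywhere from 30% to 70%, the shift is 1.5 to 3.5 points at q = 5%, 3 to 7 at 10% and 6 to 14 at 20%. If only a fraction c of prior users continues beyond 6 months, the shift is q × (c − p). It vanishes if they continue no more often than new starters.

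**4. Against sampling error.** The 95% half-width is 1.96 × √(o(1 − o)/n), with o the reported share. For o from 43% to 52% it is about 3.1 points at n = 980, 1.8 at 2940 and 1.4 at 4900. These n are all VTE cases; the treated men are fewer and the true half-widths wider. Under these assumptions, a shift at q of 10% or more is larger than the sampling error in the table's 1%, 3% and 5% scenarios, and a larger cohort does not reduce it.

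**5. Objectives 5 to 7.** No size can be given. The last column of the table shows how far the longest-duration stratum could consist of prevalent use. The direction of the effect on each rate is not fixed.

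**The case against.** Six arguments stand on the other side.

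- **These men are partly identified.** A reader might infer that they are invisible to the plan. The document does not support that: AF and previous VTE are recorded at prostate cancer diagnosis. What stands is that this flag does not show anticoagulant use, misses AF arising before the VTE, and is not used in Objectives 4 to 7.
- **The 90-day rule separates new from continuing use.** It is the nearest thing to such a rule, but it is not tied to the VTE date. If it is applied there, a man who refills regularly has no new start after his VTE, and the plan does not say how he is then counted.
- **Continued use is real exposure.** This is correct. A man who stays on a VKA after a DVT is anticoagulated, and a change of drug after the VTE is a post-VTE choice. Objective 4 can be read as treatment received, whatever the reason. The difficulty arises when its duration is read as duration of VTE treatment, as 9.10 invites.
- **The study is descriptive and compares no drugs.** 9.8 says so, and this limits the consequence. It does not protect the share beyond 6 months, which is itself a primary descriptive result.
- **Initiation appears only in the background.** Section 7 lists general gaps, the objectives do not use the term, and time at risk in 9.8 runs from the VTE. This stands. The point about initiation therefore concerns what may be concluded from the rates, not a breach of an objective.
- **An SAP could add a flag.** It could, since dispensing data are linked from July 2005 (9.5). But the variable list, the exposure start and the strata are set in the Protocol, and none of them calls for one.

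**Conclusion.** The point holds in limited form. AF and previous VTE are recorded at prostate cancer diagnosis. Anticoagulant use immediately before the VTE is not a listed variable, and nothing in Objectives 4 to 7 separates it from treatment started for the VTE. The share treated beyond 6 months can therefore be too high, and the post-VTE rates by drug and duration can mix prevalent with new use.

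The overstatement of 3 to 12 points is an illustration. It rests on three assumptions without support in the document: 5% to 20% prior use, full continuation beyond 6 months, and a true share of 40%. It should not be cited as an estimate of the bias.

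A reader might also infer that new users should replace the full sub-population as the main analysis set. The document does not support that: the study is a population description with no exclusions, and such a change would alter its target population. The plan's results stand as a description of drugs dispensed after a VTE; the separation is a cheap improvement to make before analysis.

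**What to change.** **In 9.3**, add a flag for any anticoagulant fill before the VTE date, and update AF status to that date. The look-back should match the six-month refill-gap rule in 9.4.3. The figure of 120 used for co-medications has no unit in 9.3.1 and, read as days, would conflict with that rule. A man with fills 150 days before and 10 days after the VTE has a gap of 160 days, so 9.4.3 treats him as continuously exposed, while a 120-day window would call him new. With a six-month window, any man whose last earlier fill lies outside it begins a new treatment period under 9.4.3. Dispensing data from July 2005 cover this window for every man diagnosed from 2007.

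**In 9.8**, keep the full VTE sub-population as the overall description. In addition, report duration and drug choice (Objective 4) and the results for Objectives 5 to 7 separately for new users and prior users. Base any statement on the duration of VTE treatment, or on risk after initiation, on the new-user stratum.

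**Cost:** one derived flag from data already linked, extra table rows, and wider intervals within strata. No new data and no exclusions are needed.

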8.1 Primary objective

Among all men with PCa:

- To describe socio-demographic and clinical characteristics at the date of an incident PCa diagnosis.
- To estimate the occurrence of cancer-related VTE.
- To describe the cancer therapies in PCa at the initial time after diagnosis.

Among men with PCa and a first cancer-related VTE event:

- To characterize the long-term anticoagulation treatment including choice of drug and duration of treatment.
- To estimate the occurrence of recurrent VTE events by long-term anticoagulation treatment (LMWH, VKA or NOAC) and its estimated duration (up 3 months, 3-6 months, more than 6 months).
- To determine the time between a first cancer-related and a recurrent VTE event.
- To estimate the incidence rates of post-VTE bleeding events leading to hospitalization, and mortality by anticoagulation treatment.

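### Post-VTE event rates are stratified by achieved anticoagulation duration while time at risk starts at the VTE, so the long-duration death rate contains guaranteed death-free time and every duration stratum is open to bias

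*Protocol*

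**What the plan says.** Section 9.8 fixes the clock: "Time at risk for Objectives 5, 6 and 7 (recurrent VTE, bleeding leading to hospitalisation or death) will be calculated from first cancer-related VTE", and it runs "for each events of interest up until event, death or end of follow-up". The same section fixes the strata: "Incidence rates of recurrent VTE, bleedings and death will be calculated by the type and duration of AC treatment (stratification variables". The classes appear in the Objective 4 sentence of 9.8 as "from the time-point of a hospital discharge up to 3 months, 3-6 months, more than 6 months".

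The request for duration strata has two sources. For recurrence it is Objective 5 in section 8.1: "To estimate the occurrence of recurrent VTE events by long-term anticoagulation treatment (LMWH, VKA or NOAC) and its estimated duration". For bleeding and death it is the analysis text only (the abstract's data analysis row and 9.8); Objective 7 names anticoagulation treatment but not duration.

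Duration is derived from dispensings after the VTE (9.4.1 and 9.4.3). Under the refill method, treatment ends three months after the last recorded dispensing. Section 9.4.1 sets the exposure start differently from the 9.8 clock: "A start date will be defined as the date of the dispensed prescription for patients receiving anticoagulation". The protocol mentions no landmark, delayed entry or time-updated duration, and the limitations in 9.10 do not mention the issue.

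**The concern.** Men are classified by something that happens after their clock starts. To be in the over-6-month class a man must still be alive when that duration is reached, so the class cannot contain an early death, yet its denominator contains the early person-time. A man who dies at month 2 is placed in the up-to-3-month class because he died. This is immortal time.

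Recurrence is affected under a primary objective, and bleeding and death under the planned analysis of another. Section 7 names treatment beyond 6 months as an area without reliable data and says the evidence will support treatment decisions, so readers will look across the duration classes. Even read singly, the outer strata do not estimate the death rate of the men they appear to describe.

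**Working it through.** **Inputs from the protocol.** Time at risk starts at the VTE and ends at event, death or end of follow-up; class limits are 3 and 6 months (9.8). The protocol states no post-VTE rate by duration, so there is no figure of its own to reproduce.

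**Assumptions, not from the protocol.** Constant death rate λ, the same for every man whatever his treatment (no true effect). Treatment starts at the VTE. Achieved duration is the smallest of planned duration, time to death and time to administrative end. Administrative end is uniform over 1-10 or 0.5-6 years. Planned duration is either exponential (mean 6 or 12 months) or a fixed mix over the three classes, uniform within each class (top class up to 2 years).

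**Step 1: the over-6-month class in closed form (follow-up 1-10 years).** Each man in it contributes 0.5 death-free years. After that he dies under observation with probability

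p = 1 − (e^(−0.5λ) − e^(−9.5λ)) / (9λ)

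and contributes p/λ further years on average. The stratum rate is p / (0.5 + p/λ).

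For λ = 0.20: p = 1 − (0.9048 − 0.1496)/1.8 = 0.580, and the rate is 0.580/(0.5 + 2.902) = 0.171, that is 17.1 per 100 person-years against a true 20. The same formula gives 4.5, 8.8 and 31.8 for true rates of 5, 10 and 40. Without the 0.5 guaranteed years the rate is exactly λ.

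**Step 2: all three classes by simulation (1-2 million men per scenario).** Death rates per 100 person-years:

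| Planned duration | Follow-up (years) | True rate | Up to 3 | 3-6 | Over 6 | Over 6 / up to 3 |
|---|---|---|---|---|---|---|
| Exponential, mean 6 months | 1-10 | 5 | 5.4 | 5.2 | 4.5 | 0.83 |
| Exponential, mean 6 months | 1-10 | 20 | 22.3 | 20.7 | 17.1 | 0.77 |
| Exponential, mean 12 months | 1-10 | 20 | 25.4 | 23.3 | 17.1 | 0.67 |
| Exponential, mean 12 months | 1-10 | 40 | 55.4 | 47.7 | 31.8 | 0.57 |
| Mix 20/30/50% | 0.5-6 | 20 | 28.3 | 21.1 | 15.9 | 0.56 |
| Mix 10/20/70% | 0.5-6 | 20 | 38.5 | 24.4 | 15.9 | 0.41 |
| Mix 10/20/70% | 0.5-6 | 40 | 85.8 | 49.2 | 30.0 | 0.35 |

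The over-6-month class contains no death before 6 months in any run. The middle class can fall on either side of the true rate, so the directional statement concerns the outer two.

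**Step 3: the refill rule.** If the three-month tail after the last dispensing is not cut at death, the over-6-month class still needs a dispensing more than 3 months after treatment starts. The guaranteed death-free time is then at least 3 months instead of 6. The mechanism stays; its size under that reading was not computed.

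**Step 4: recurrence and bleeding.** Neither event has to end treatment. If duration stops at the event, the arithmetic above applies. If a recurrence prolongs treatment and the later dispensings count, the bias reverses: at a true rate of 20 with mean duration 6 months the classes give 19.2/17.9/22.2, and over the exponential scenarios the ratio is 1.06-1.22.

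**Step 5: the remedies.** Under the same null assumptions, a 6-month landmark and time-varying allocation both return about 20/20/20 at a true rate of 20. The landmark ratio is 1.00-1.01 across the exponential scenarios.

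**The case against.** The strongest defence is that the study is descriptive and 9.8 disclaims comparison. That disclaimer covers the three anticoagulant types and does not mention the duration classes. Nor does it help a rate that is wrong on its own. A second defence is that splitting person-time by window is ordinary detail for a statistical analysis plan. That would be fair had the protocol left the matter open, but 9.8 fixes both the VTE origin and duration as a stratification variable. The on-treatment definition in 9.4.1 does not cure the duration strata: when follow-up stops with treatment, the null ratio in the exponential scenarios falls to 0.08-0.12.

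Four stronger readings are tempting and are not supported:

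- A reader might infer that long treatment will look protective for every outcome. That is structural only for death. Section 9.4.1 continues follow-up for other outcomes after a first event, and under 9.4.3 later refills add treatment time, so recurrence and bleeding can go either way.
- A reader might infer that Objective 7 asks for duration strata. It does not.
- A reader might infer that the rates by drug type are equally flawed. The dispensing start date in 9.4.1 can avoid the gap from VTE to first dispensing, so this is not established.
- A reader might see three contradictory time origins. Hospital discharge appears only in the treatment description for Objective 4, and an exposure clock may differ from a risk clock. What remains is that 9.8 and 9.4.1 do not say which origin governs the treatment-stratified rates.

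**Conclusion.** The point holds for the duration strata. Followed as written, 9.8 gives a death rate that is too low in the over-6-month class and too high in the up-to-3-month class when treatment has no effect. The spurious ratio is about 0.35-0.83. It rests on assumed constant death rates of 5-40 per 100 person-years, assumed duration mixes and follow-up, and duration that stops at death. The existence and direction of the bias for death do not depend on those choices; its size does. For recurrent VTE and bleeding the rates are biased too, in a direction the protocol leaves undetermined. Because the results feed primary objectives, the wording should be changed before the analysis is run.

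**What to change.** In 9.8, remove the strata of final total duration and use one of two replacements:

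1. **Time-varying duration.** Start person-time at the first out-patient dispensing after the VTE. Split it by treatment time accrued so far (0-3, 3-6, more than 6 months) and by on or off treatment. Count each event in the interval where it occurs.
2. **Landmarks at 3 and 6 months.** Take men event-free at the landmark, class them by treatment up to it, and follow them forward from it.

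State one time origin for the treatment-stratified rates and make 9.4.1 agree with it. Bring Objective 7 and the analysis text into line on whether bleeding and death are reported by duration.

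The cost is wording in 9.8 and 9.4.1 and slightly more programming; no new data are needed. The landmark version drops events before the landmark.

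### Recurrence, bleeding and death after a first cancer-related VTE are listed only by dispensed anticoagulant, so men without a fill have no stratum and pre-fill days enter the treated denominators

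*Protocol*

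**What the plan says.** Protocol 8.1 sets Objectives 4 to 7 in one population: "Among men with PCa and a first cancer-related VTE event". For men with prostate cancer, 9.2.3 states "No exclusions will be made", so no pharmacy fill is needed to belong to it.

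Objective 5 reads "To estimate the occurrence of recurrent VTE events by long-term anticoagulation treatment (LMWH, VKA or NOAC) and its estimated duration". Objective 7 reads "To estimate the incidence rates of post-VTE bleeding events leading to hospitalization, and mortality by anticoagulation treatment". Section 9.8 carries this into the analysis: "Incidence rates of recurrent VTE, bleedings and death will be calculated by the type and duration of AC treatment (stratification variables"). It adds "however no comparative analysis of outcomes in three sub-groups of AC treatments, is planned". The same section starts time at risk for Objectives 5, 6 and 7 at the first cancer-related VTE.

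Exposure is seen only through pharmacy dispensing. Section 9.3.2 says "no information is available on drugs delivered in- hospital", and 9.4.1 dates the start of exposure from the dispensed prescription. Section 9.10 admits the in-hospital gap and answers it by saying that, "given that treatment for VTE is usually a minimum of three months will be captured by the ensuing out-patient treatment".

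**The concern.** Population, time zero and strata do not fit together. A man who dies in hospital after his pulmonary embolism, is anticoagulated only in hospital, or never fills a prescription is one of the men the objectives describe, yet he belongs to none of the three drug classes. The reply in 9.10 relies on a later out-patient fill, which cannot exist for a man who dies before it.

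Men who do fill are followed from the VTE but classified by something that happens later. Their interval from VTE to first fill is free of death by construction, yet it counts as time at risk in the drug stratum.

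Mortality, bleeding and recurrence after VTE are primary-objective outcomes. If only the listed strata are tabulated, fatal events before a fill appear in no rate, and a reader may take the stratum rates as describing all men with cancer-related VTE.

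**Working it through.** The protocol gives no figure for this point. Its one precision table (9.6) concerns VTE incidence in 98 000 men and does not bear on Objectives 5 and 7. The structural check comes first, then illustrations on assumed inputs.

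**1. Where each man goes under 9.8 as written**

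| Man with a first cancer-related VTE | In the population (8.1, 9.2.3) | In a listed stratum (9.8) |
|---|---|---|
| Fills LMWH, VKA or NOAC | yes | yes, with time counted from the VTE |
| Dies before any fill | yes | no |
| Survives, treated only in hospital | yes | no |
| Survives, never fills | yes | no |

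**2. Days before the first fill.** In a drug stratum, let *D* be deaths, *P* the person-years from first fill and *G* the person-years from VTE to first fill. Every death falls after the fill. Counting from the VTE gives *D*/(*P* + *G*); counting from dispensing gives *D*/*P*. The first is smaller whenever *G* > 0, by the factor *P*/(*P* + *G*). No assumption about who fails to fill is needed. The protocol does not give *G*: the effect is small if fills follow within days and larger after long admissions. The argument holds for death. A non-fatal bleed or recurrence can precede the first fill in a man who fills later, so for those outcomes the direction is not fixed.

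**3. Men with no stratum: one-year risk (assumed inputs).** Assume 30% one-year mortality in all VTE men, a share *d* dying before any fill, and no man surviving without a fill. The risk in the strata together is (0.30 − *d*)/(1 − *d*):

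- *d* = 0.05: 0.25/0.95 = 26.3%
- *d* = 0.10: 0.20/0.90 = 22.2%
- *d* = 0.15: 0.15/0.85 = 17.6%

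**4. Men with no stratum: person-year rates (assumed inputs).** Section 9.8 specifies rates, so the same question is put in that form. Per 1,000 men, a share *f* has no fill; a share *q* of these die early, on average 15 days after the VTE; all other men die at rate λ per year over one year. A man at rate λ has death probability 1 − e^(−λ) and expected person-years (1 − e^(−λ))/λ.

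For λ = 0.10, *f* = 0.10, *q* = 0.25:

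- Men with a fill: 900 × 0.0952 = 85.6 deaths in 900 × 0.952 = 856.5 person-years, or 10.0 per 100.
- Men without: 25 + 75 × 0.0952 = 32.1 deaths in 25 × 15/365.25 + 75 × 0.952 = 72.4 person-years.
- All men: 117.8/928.9 = 12.7 per 100. The strata show 0.79 of this.

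| λ | *f* | *q* | Strata, per 100 person-years | All VTE men | Ratio |
|---|---|---|---|---|---|
| 0.10 | 0.10 | 0.25 | 10.0 | 12.7 | 0.79 |
| 0.20 | 0.10 | 0.25 | 20.0 | 22.8 | 0.88 |
| 0.10 | 0.20 | 0.50 | 10.0 | 21.6 | 0.46 |
| 0.20 | 0.20 | 0.50 | 20.0 | 32.1 | 0.62 |

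With both values of λ, *f* from 5% to 30% and *q* from 25% to 50%, the ratio runs from 0.35 to 0.94 at one year and from 0.60 to 0.97 at three years. The effect in step 2 is left out of these figures.

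**5. Can the direction reverse?** Yes. Let surviving men without a fill die at half the rate (10 against 20 per 100 person-years) over one year, with *f* from 10% to 30%. The ratio is 1.02 to 1.07 at *q* = 5% and 0.98 to 0.99 at *q* = 10%. The strata then overstate all-men mortality while fewer than about 9% of men without a fill die early.

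**The case against.** The strongest reply is that 9.8 first sets time at risk for the whole VTE sub-population and only then names drug type and duration as stratification variables. Overall rates, then stratified, is a natural reading, and total and no-treatment rows are table details that an analysis plan often supplies. The mention of three sub-groups stands in a clause disclaiming comparison and is not a list of rows. This stands in part: the protocol nowhere rules out an overall rate, and 'only' is inferred from the outputs it names. But the abstract, 8.1 and 9.8 all word the bleeding and mortality output by treatment, and 9.8 itself fixes a time zero that does not match the classification. For recurrence, Objective 6 in 8.1 is not split by treatment, although the abstract splits it.

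A reader might also infer that the share of men with no out-patient anticoagulant will go unreported. The protocol does not support that. Objective 4 describes treatment among all men with a first cancer-related VTE, and 9.8 reports categorical variables as counts and proportions, so the share may be available as the remainder.

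A rate among men dispensed a given drug is not in itself a wrong estimate of mortality in all VTE men, because the two are different quantities. That is correct, and steps 3 and 4 compare exactly those two. The protocol does not say that the strata will be pooled and presented as whole-population mortality.

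Finally, 9.4.1 dates exposure from dispensing. If that also governed time at risk, the denominator effect would vanish. Section 9.8 says otherwise, and events before the first fill would still be counted nowhere.

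**Conclusion.** The mismatch stands on the protocol's text. Men who die before a fill or never fill belong to the population of Objectives 5 and 7 but to no listed stratum, and pre-fill days lower the death rates of the drug strata. The listed rates therefore do not describe outcomes in the whole VTE sub-population and are likely to understate early mortality.

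Two limits apply. The lowering of stratum death rates by pre-fill days follows from the definitions alone. Understatement relative to all VTE men does not: it assumes that men without a fill die more often. That is likely, since early and in-hospital deaths are among them, but it is not shown. Nor can the size be derived from the protocol. A reader might take the fall from 30% to 26%, 22% or 18% as the bias to expect. It is an illustration in which both the mortality and the pre-fill deaths are assumed and no man survives without a fill.

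**What to change.** In 9.8, add an exposure category for no out-patient anticoagulant dispensed. It should hold men who never fill, and the person-time and events before the first fill of men who do, so that person-time in each drug stratum starts at dispensing. Alongside the strata, report one overall unstratified rate each for recurrence, bleeding and death in the whole VTE sub-population, counted from the VTE. Add to 9.10 that later fills cannot capture men who die before a fill or never fill.

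The cost is one category and one total row per table, from data already held. The drawback is that the new category mixes men treated only in hospital with untreated men, and early pre-fill days with long-term non-use; a footnote should say so.

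Starting at dispensing does not by itself settle the duration strata: a man classed as treated for more than 6 months must have survived about that long. Duration needs the same care when the strata are defined.
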